### **Secondary objectives:**

- To study the effect of IPC on the asymptomatic venous thrombosis occurrence during inpatient treatment in prespecified groups of patients:
  - Surgical profile,
  - Type of surgery,
  - The urgency of surgery,
  - The radicalism of surgery,
  - Type of anesthesia,
  - Malignant or benign disorder;
  - Preoperative, postoperative or delayed start of LMWH injections,
  - Pre-operative or post-operative IPC application,
- To study the effect of IPC on the isolated calf muscle DVT occurrence during inpatient treatment;
- To study the effect of IPC on the proximal DVT occurrence during inpatient treatment;
- To study the effect of IPC on the symptomatic PE occurrence during inpatient treatment;
- To study the effect of IPC on the fatal PE occurrence during inpatient treatment,

- To study the effect of IPC on the total VTE events that occur during inpatient treatment,
- To study the effect of IPC on the leg skin injury occurrence during inpatient treatment;
- To study the effect of IPC on the major and clinically relevant non-major bleeding occurrence during inpatient treatment;
- To study the compliance with IPC applied in the suggested regimen-required night free-of-compression interval;
- To study the effect of IPC on the symptomatic and asymptomatic venous thrombosis of lower limbs, symptomatic pulmonary embolism occurrence, and VTE related and VTE-non-related mortality during outpatient treatment and rehabilitation 30 and 180 days after surgery.

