#### **4.2. Low-molecular-weight heparins**

Standard doses of 40 mg Enoxaparin (Clexane, Sanofi-Aventis, France) subcutaneously once daily is prespecified. Following Russian National Guidelines, the first injection should be done 12 h before the surgery (elective surgery without high bleeding risk) or within 12 h after surgery (emergent surgery, procedure with high bleeding risk). In the case of the highest bleeding risk, it is allowed to delay the first LMWH injection for 5 days. The patients who did not receive Enoxaparin after 5 days will be withdrawn from the analysis. The pharmacoprophylaxis should be continued until the patient's discharge from the hospital (not less than 7 days) or death. The prolonged prophylaxis with LMWH is not pre-specified and will depend on the surgeon's preference. The enoxaparin administration and the control for injection should be made within the standard clinical practice.

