## 8. Statistical analysis plan and sample size calculation

**Statistical analysis plan.** The primary statistical analysis is designed as intention-to-treat with the use of two-tailed Fisher's exact test to compare the primary endpoint between two groups. The primary endpoint will be reported as an absolute number, percentage, and relative risk with 95% CI. Secondary statistical analysis of the primary endpoint will be made using an unadjusted Cox proportional-hazards model. The data will be censored on the time of VTE registration, or death, or discharge from the hospital and reported as a hazard ration with 95% CI. Kaplan-Meier curves will be used to compare time-to-event distribution. Cox proportional-hazards models adjusted for the clinical center, surgery profile, type of surgery, emergency of surgery, type of anesthesia, surgical radicalism, malignant disorder, Caprini score, and time to start LMWH injections will be used.

A similar analysis for the per-protocol population, but that excluded patients with gross violations of the protocol and premature discontinuation of at least one component of combined prophylaxis (ECS, IPC or LMWH), will be performed for the primary endpoint.

Secondary endpoints will be analyzed with two-tailed Fisher's exact test and will be represented as an absolute number, percentage, and relative risk with 95% CI.

Cox proportional-hazards models will be used for the prespecified subgroup analysis for the following subgroups: surgical profile; type of surgery; the urgency of surgery; the radicalism of surgery; type of anesthesia; malignant or benign disorder; preoperative, postoperative, or delayed start of LMWH injections; and pre-operative or post-operative IPC application.

Sensitivity analysis will address to the per-protocol analysis, compliance with IPC (restricted for 90% and more), duration of follow-up (restricted to 7 days and more), and the number of postoperative DUS (restricted with two and more).

Missing data on the primary endpoint are not anticipated in the inpatient settings, so no analysis for missing data being planned.

Adjusting for multiple comparisons and imputation for missing values will not be performed. The 95% confidence intervals will be not adjusted for multiplicity, and therefore, inferences drawn from these intervals might be not reproducible. The interim analysis is not planned.

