**Sample size calculation.** The prevalence of asymptomatic postoperative vein thrombosis at the top of standard prophylaxis with ECS and LMWH was assumed as 30% based on our previous observations involving patients at high and extremely high risk. Taking into account the fact that pharmaco-mechanical prophylaxis should provide a further 60% VTE risk reduction, the absolute difference of 18% is assumed. Using Fisher's exact test for primary statistic analysis, with a power of 80% and type I error of 0.05, the sample size is estimated as 180 subjects (90+90 in each group). Assuming 10% withdrawal due to the protocol deviations, patient's decision, or incomplete data, the sample size is calculated as 200 subjects. Considering prespecified subgroup analysis for the patients with an early and delayed start of LMWH, we decided to double the sample size to achieve sufficient power for separate analyses of the suggested subgroups. IBM SPSS will be used for data processing.

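### The sample is doubled to power separate analyses by LMWH start time, but no subgroup shares are given; at the plan's own 30% v 12%, a subgroup holding one third of patients or fewer has less than 80% power.

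*Combined protocol and SAP*

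**What the plan says.** The sample size paragraph of section 8 assumes 30% asymptomatic thrombosis in controls and a 60% relative reduction with IPC, so 12%. It plans Fisher's exact test "with a power of 80% and type I error of 0.05" and arrives at 90 per arm, 180 in all, raised to 200 for 10% withdrawal. The next step is the doubling: "we decided to double the sample size to achieve sufficient power for separate analyses of the suggested subgroups". Two subgroups are meant, those who start LMWH early and those who start it late. The doubled total is not printed; it is 400 randomised, or 360 evaluable after the same 10% loss.

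The timing groups are described differently elsewhere. The secondary objectives in section 2 list "Preoperative, postoperative or delayed start of LMWH injections", and the analysis plan in section 8 lists "preoperative, postoperative, or delayed start of LMWH injections". Both give three groups where the sample size paragraph gives two. The method for subgroups is also not the one used for sizing: "Cox proportional-hazards models will be used for the prespecified subgroup analysis for the following subgroups".

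Section 4.2 ties timing to the type of surgery and bleeding risk: "the first injection should be done 12 h before the surgery (elective surgery without high bleeding risk) or within 12 h after surgery", the latter for emergent surgery or procedures with high bleeding risk. A delay of up to 5 days is allowed only at the highest bleeding risk, and patients with no enoxaparin after 5 days leave the analysis. Allocation in section 3.1 uses the medical record number, without stratification by LMWH timing.

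**The concern.** Doubling a sample gives each of two subgroups the original power only if they are close to equal in size. The plan neither states nor justifies such a split, and the rule for delayed start in section 4.2 gives no reason to expect one. If the three listed groups are analysed, the smallest cannot hold more than a third of the patients.

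What is at stake is interpretation. A protocol that declares its subgroup analyses adequately powered invites a reader to take a non-significant result in the smaller timing group as absence of benefit there. The caution in section 8 that "inferences drawn from these intervals might be not reproducible" is about unadjusted multiplicity and does not warn of low power.

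**Working it through.** **Inputs from section 8.** Control 30%, IPC 12%, two-sided alpha 0.05, power 80%, 1:1 allocation, N = 400 randomised or 360 evaluable. Subgroup shares are not in the documents, so every share below is an assumption. The same 30% v 12% is applied in each subgroup.

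**1. The plan's own figure.** The two-proportion formula with continuity correction gives 90 per arm, so 180; 180 / 0.90 = 200. Exact power of the two-sided Fisher test at 90 per arm, by full enumeration of both binomials, is 81.2%. The base figure reproduces.

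**2. Doubling with an equal split.** Each half has 90 per arm (N = 360) or 100 per arm (N = 400). Fisher power is 81.2% or 85.4%, so the plan's reasoning works in this case.

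**3. Smallest share that gives 80%, Fisher.** Power is 79.5% at 87 per arm and 80.1% at 88 per arm. The subgroup needs 2 × 88 = 176 patients: 176/360 = 49%, 176/400 = 44%.

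**4. Smallest share that gives 80%, Cox.** Under proportional hazards, HR = ln(0.88)/ln(0.70) = 0.358. Schoenfeld: events = 4(1.960 + 0.842)² / (ln 0.358)² = 29.8. The average event risk is (0.30 + 0.12)/2 = 0.21, so patients = 29.8/0.21 = 142: 142/360 = 39%, 142/400 = 36%. The formula is optimistic with so few events. A simulated Cox Wald test (6,000 runs, constant hazards, an assumed common 10-day follow-up) needs about 160 patients: 44% of 360, 40% of 400.

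**5. Power by assumed share** (first figure N = 360, second N = 400). Schoenfeld power = Φ(½√d · |ln HR| − 1.96), with d = 0.21 × subgroup size.

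| Share | Events | Fisher | Cox, Schoenfeld | Cox, simulated |
|---|---|---|---|---|
| 40% | 30–34 | 71–76% | 81–84% | 76–80% |
| One third | 25–28 | 60.5–67.3% | 73–78% | 66–72% |
| One quarter | 19–21 | 46–52% | 61–65% | 53–58% |
| 20% | 15–17 | 37–42% | 51–56% | not run |
| 15% | 11–13 | 24–29% | 41–44% | 25–32% |

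**6. Three groups.** The smallest of three holds at most one third. At 30% v 12% it is therefore below 80% by every method above, whatever the split.

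**7. Sensitivity to control risk.** One-third share, same 60% reduction:

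| Control v IPC | Fisher | Cox, Schoenfeld |
|---|---|---|
| 20% v 8% | 38–43% | 52–57% |
| 35% v 14% | 71–77% | 81–85% |
| 40% v 16% | 79.4–84.5% | 88–91% |

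**8. Overall comparison.** Fisher power is 98.6% at 180 per arm and 99.3% at 200 per arm.

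**The case against.** The strongest reply is that nothing has been miscalculated. The sample size paragraph names two groups, and for two equal groups doubling is correct. It does not define early and delayed. If early meant preoperative only, delayed could take in every postoperative start, including emergency patients, and the split might be near even. The three-group list carries no power claim of its own. The control risk may also be too low: section 1 reports 59% VTE at Caprini scores of 11 or more. At 59% v 23.6%, a one-third subgroup has Fisher power of 97–98% and a one-fifth subgroup 81–87%. Finally, subgroups are secondary and the main comparison loses nothing.

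Part of this stands. The fault is an unsupported design claim rather than an error in the base arithmetic; an even split would deliver the power; and a higher control risk would raise it.

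The rest does not remove the point. Sections 2 and 8 list delayed start separately from postoperative start, and section 4.2 limits delay to the highest bleeding risk, so the broad reading of delayed goes against the plan's own terms. The 59% was observed with unfractionated heparin and counts symptomatic events; the plan chose 30% as its design rate, and its power claim has to be judged at that rate.

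**Conclusion.** The concern holds. The stated reason for the second 200 patients is a subgroup power that the plan does not show and the design does not secure. With two groups, the smaller must hold about 44–49% of patients by Fisher, or 36–39% under Cox by Schoenfeld (40–44% by simulation), to reach 80%. With the three listed groups, the smallest falls short in any split: at best 61–67% by Fisher and 73–78% by Cox (66–72% simulated).

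This rests on 30% v 12% in every subgroup, 1:1 allocation within subgroups, 360 to 400 patients analysed, and 80% as the meaning of sufficient, since it is the only power standard the plan states. It concerns the separate within-subgroup comparisons that the plan describes, not an interaction test. The primary comparison is not affected. The matter should be corrected but does not threaten the trial's main conclusion.

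**What to change.** In section 8:

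- State the final N (400) and the number expected to be evaluable (360).
- Use one set of LMWH-timing groups in the section 2 objectives, the subgroup list and the sample size paragraph, with definitions and expected shares.
- Withdraw the claim of adequate power for separate analyses, or replace it with power by assumed share under the planned Cox model.

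Possible wording:

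> At 30% v 12% and with 360 to 400 patients analysed, a timing subgroup with one third of patients has about 66–78% power under the Cox model, and one with a quarter about 53–65%. The LMWH-timing subgroups are exploratory and are reported as hazard ratios with 95% CI; a non-significant subgroup result is not evidence of no benefit.

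These ranges run from the simulated value at 360 to the Schoenfeld value at 400.

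The cost is a rewording of section 8, alignment of the group labels, and a less favourable stated subgroup power. No additional patients are needed.
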